8.3. Halting Criteria for the Study

The study enrollment and dosing will be stopped and an ad hoc review will be performed if any of the specific following events occur or, if in the judgment of the study physician, subject safety is at risk of being compromised:

- I. Unexpected death of a dosed subject in relation to infusion
- II. Occurrence of a life-threatening allergic/hypersensitivity reaction (anaphylaxis), manifested by bronchospasm with or without urticaria or angioedema requiring hemodynamic support with pressor medications or mechanical ventilation.
- III. One subject with an unexpected SAE associated with study product.
- IV. Two subjects with a Grade 3 or higher toxicity for the same parameter associated with study product.
- V. An overall pattern of symptomatic, clinical, or laboratory events that the medical monitor, ISM, or SMC consider associated with study product and that may appear minor in terms of individual events but that collectively may represent a serious potential concern for safety.
- VI. Any other event(s) which is considered to be a serious adverse event in the good clinical judgment of the responsible physician. This will be appropriately documented.

Interim Analyses for efficacy: There will be two formal review of interim results. The first will occur after 15 infections which is expected to occur near 150 participants reaching day 28 and the second after 50% of the total recruitment (n=500) has been achieved and these individuals followed to at least day 28. Interim analyses will only be adjusted for age. Stopping guidelines will be based on O’Brien-Flemming boundary. The interim analysis Z-value boundary of 3.03 (nominal p-value of 0.0011, spent alpha 0.0011), 2.38 (0.0087, 0.008), and 1.68 (0.464, 0.408) for a one-sided test with Type 1 of 0.05.

Special considerations for death:

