Furthermore, given that ADE may be an issue with convalescent antibody treatment, out of an abundance of caution we will monitor the number of subjects in each trial arm that progresses to death. Given that we plan to recruit 75 participants in each arm and with the following assumptions 1) 20% of those in standard arm progress to symptomatic infection, 2) 5% in the anti-SARS-CoV-2 treatment arm are expected to progress to symptomatic infection, and 3) 1.4% of those with symptomatic infection progress to death, the probability of observing one death in either arm is unlikely (Table 1). Even with a higher symptomatic case fatality rate of 2.7% that has been estimated for those >64 years in Wuhan, China (Table 1) [Wu JT, LeungK, Bushman M, et al. Estimating Clinical Severity of COVID-19 from the transmission dynamics in Wuhan, China. *Nature Med*]. However, it is possible that more than one death may be seen by random chance in the sample that we accrue. Therefore, we will monitor the number of subjects that die and thoroughly evaluate whether each death is likely due to anti-SARS-CoV-2 plasma (definite, probable, possible, or unlikely). The DSMB will be unmasked for all interim analyses and reviews for safety. It is likely if 2 deaths occur in intervention arm that the DSMB would need to consider stopping due to safety concerns as two deaths would be highly unlikely (Table 2). After at least 50% of trial participants have accumulated follow-up, the number of subjects that progress to this stage will be presented to the masked DSMB and formally asked whether they see a clinically meaningful difference between trial arms that trigger an unmasking of the DSMB. This interim safety analysis will adjust for factors related to mortality including age and presence of cardiopulmonary comorbidities.

Table 1: Binomial probability of at least one death among each treatment arm by overall symptomatic case fatality rate and for those >64 years of age as estimated in Wuhan, China

Symptomatic Case Fatality Rate	Standard Plasma arm Expected Symptomatic N=15 participants	Anti-SARS-CoV-2 Plasma arm Expected Symptomatic N=4 participants
1.4%	0.191	0.055
2.7%	0.337	0.10

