Table 2: For 1, 2, or 3 deaths observed among the expected number of symptomatic cases, the event probability of death (95% CI) and the probability that this would be observed under the overall symptomatic case fatality rate of 1.4% from Wuhan, China

	Standard Plasma Arm			Anti-SARS-CoV-2 Plasma arm		
	# of deaths	Point Estimate of Mortality	95% Confidence Interval	Probability of occurring under true symptomatic case fatality rate of 0.014	Point Estimate of Mortality	95% Confidence Interval
1	0.07	(0.002, 0.319)	0.19	0.25	(0.006, 0.806)	0.05
2	0.13	(0.017, 0.405)	0.018	0.50	(0.068, 0.932)	0.001
3	0.20	(0.043, 0.481)	0.001	0.75	(0.194, 0.993)	<0.0001

Special considerations for ARDS: Given that ARDS is a significant potential consequence of COVID-19 and potentially a sign of ADE, we will monitor participants for development of ARDS as a medical consequence of concern by monitoring differences between participants receiving control plasma and anti-SARS-CoV-2 plasma. Given that we plan to recruit 75 participants in each arm and with the following assumptions 1) 20% of those in standard arm progress to symptomatic infection, 2) 5% in the anti-SARS-CoV-2 treatment arm are expected to progress to symptomatic infection, and 3) in an abundance of caution *as a worst case scenario* we will assume that 40% will progress to ARDS (in Wuhan the reported frequency of ARDS was 3.4% for all subjects and 40% among the group reaching the composite endpoint of ICU admission, ventilation or death). Under this scenario of assumed maximum severity, we are likely to see at least one case in both treatment arms (Table 1). Specifically, we would expect *six* participants in the control and *two* participants in the treatment arm to develop ARDS (table 4). After at least 50% of trial participants have accumulated follow-up, the number of subjects that progress to this stage will be presented to the masked DSMB and formally asked whether they see a clinically meaningful difference between trial arms. This interim analysis will adjust for factors related to worsening of COVID-19 such as age, prior lung disease, and presence of cardiopulmonary comorbidities.

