## Randomization

The Data Coordinating Center (DCC) will work with the EDC developers (Prelude Dynamics) to generate random treatment assignments using a documented process. The randomization schedule will be designed to yield an expected allocation ratio of 1:1 for HCP + control plasma. Assignments will be stratified by clinical site and schedules will employ permuted block designs, with block sizes to be determined and documented at the DCC. Adjustment for residual or other imbalances in the baseline composition of the treatment groups, if needed, will be done using multiple regression techniques rather than through further stratification in the design.

Treatment assignments will be masked to the participants and the personnel of the clinical sites, but not to an unmasked statistician associated with the DCC. This unmasked statistician will only provide unmasking information (1) to the DSMB, (2) if required for participant safety, and (3) to the analytical team after databases have been locked. Unforeseen circumstances that may require unmasking will need to be approved by the Steering Committee. Staff in the blood banks will also be unmasked to treatment assignments

Treatments will be assigned at the baseline visit using an online program accessible to the clinical sites. After the entry of specified pre-randomization data, each enrolled participant's ID will be irrevocably linked to the next unassigned treatment for that clinical site. Upon notification of a randomization, an unmasked email is sent to the blood bank informing of the participant identifier and the treatment group assignment. Blood bank personnel will select an appropriate unit of plasma for transfusion and will mask (over-label) the unit consistent with local and federal regulations. The data system will also check for and prevent duplicate assignments (same participant randomized more than once). The treatment assignment tables in the data system will be encrypted to prevent inadvertent disclosures.

The procedures related to randomization of participants at the clinical sites will be as follows:

- Clinical sites will collect randomization eligibility and baseline data on the appropriate data collection instruments and will enter these data into the database.
- The data system will confirm randomization eligibility, issue the next assignment, and will relay treatment assignments to the DCC (masked) and blood bank (unmasked) as described above.

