## **Adverse events of study treatment:**

We hypothesize that participants randomized to convalescent plasma will not have any increased risk to standard transfusions. Preliminary data from the expanded access protocol for treatment of COVID-19 by convalescent plasma among those with severe disease, suggests that the treatment is safe with low number of adverse events [Joyner et al, J Clin Invest. 2020].

Adverse event data will be collected continuously throughout the trial and analyzed by treatment group at each interim analysis. We will also compare the rates of all serious adverse events (as

specified by the Health and Human Services definition) using cumulative incidence. The primary safety endpoints are i) the cumulative incidence of treatment-related serious adverse events categorized separately as either severe infusion reactions or Acute Respiratory Distress Syndrome (ARDS) during the study period and ii) cumulative incidence of treatment-related grade 3 and 4 adverse events during the study period.

Data collection for adverse events will be done via a combination of specific questions for anticipated effects and spontaneous participant report. We will present overall number of AEs and SAEs by treatment group and where differences exist, we will present those by organ system. As these are descriptive safety analyses no correction for multiplicity will be undertaken.

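### Protocol section 8.3 says the DSMB is unmasked for every interim and safety review, then sends the 50% death and ARDS counts to a masked DSMB

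*Protocol*

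**What the plan says.** All the protocol statements below are in section 8.3.

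- **General rule** (death paragraph): "The DSMB will be unmasked for all interim analyses and reviews for safety".
- **Two-death consideration** (same paragraph): "It is likely if 2 deaths occur in intervention arm that the DSMB would need to consider stopping due to safety concerns". It is advisory and is defined on the intervention arm.
- **50% death review** (the next sentence): the counts go to a masked board, which is asked about "a clinically meaningful difference between trial arms that trigger an unmasking of the DSMB". The protocol calls this step an interim safety analysis.
- **50% ARDS review**: the counts are "presented to the masked DSMB and formally asked whether they see a clinically meaningful difference between trial arms. This interim analysis will adjust" for prognostic factors. No unmasking step is stated. ARDS is watched because "ARDS is a significant potential consequence of COVID-19 and potentially a sign of ADE".
- **Efficacy interims**: the first comes "after 15 infections which is expected to occur near 150 participants reaching day 28 and the second after 50% of the total recruitment" with follow-up to day 28.

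The SAP describes no masked DSMB review. Its Randomization section says "This unmasked statistician will only provide unmasking information (1) to the DSMB", with participant safety as a further permitted reason. Its adverse-event section says "Adverse event data will be collected continuously throughout the trial and analyzed by treatment group at each interim analysis". Its Stopping guidelines give special attention to ARDS and deaths in the HCIP group.

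**The concern.** The protocol labels the 50% death and ARDS reviews as interim analyses, so the general rule covers both. A board that is unmasked for all such reviews cannot be masked at these two, nor be unmasked by the result of one of them. Whoever prepares the 50% safety report therefore has two incompatible instructions on what the board may see.

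The reviews exist because of antibody-dependent enhancement, a harm that could arise in only one arm. The two-death consideration applies to that arm alone. When coded arms differ modestly, the same pair of counts can be reassuring or worrying depending on which arm is which, and a masked board cannot tell.

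**Working it through.** **1. Sequence.** Half of the planned 500 is 250 participants, or 125 per arm. The first efficacy interim is expected near 150 participants, before that point. Under the general rule the board is already unmasked by then. The second efficacy interim falls at about the same 50% point as the two safety reviews, so the board would be unmasked for one review and masked for the others at nearly the same time.

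**2. Reproducing the protocol's Table 2.** Section 8.3 assumes 75 per arm, 20% and 5% symptomatic infection, and 1.4% fatality among symptomatic cases.
- Cases: 75 × 0.20 = 15 in control; 75 × 0.05 = 3.75, taken as 4, in HCIP.
- Formula: P(at least 2 deaths) = 1 − 0.986^n − n × 0.014 × 0.986^(n−1).
- Control, n = 15: 1 − 0.8094 − 0.1724 = 0.018 (stated 0.018).
- HCIP, n = 4: 1 − 0.9452 − 0.0537 = 0.001 (stated 0.001).

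**3. The same probability at the 50% review, 125 per arm.**

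| Attack rates (control / HCIP) | Cases | P(≥2 deaths), control | P(≥2 deaths), HCIP |
|---|---|---|---|
| 13% / 6.5% (section 5.1) | 16.25 and 8.1, taken as 16 and 8 | 0.021 | 0.005 |
| 20% / 5% (section 8.3) | 25 and 6.25, taken as 25 and 6 | 0.048 | 0.003 |

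Letting the number of cases vary (binomial, n = 125, p = attack rate × 0.014) gives 0.022 vs 0.006 and 0.048 vs 0.004, so the contrast does not depend on fixing the case counts.

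**4. Deaths split 2 vs 1.** The coded arms differ by one death, which a board could reasonably judge too small a difference to call for unmasking. If the 2 are in HCIP, the two-death consideration is met and the count is improbable at the assumed rates (0.001 to 0.005). If the 2 are in control, it is not met and the count is less unusual (0.018 to 0.048).

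**5. ARDS split 6 vs 2.** Section 8.3 expects six cases in control and two in HCIP (15 × 0.40 = 6; 4 × 0.40 = 1.6). That split is the expected pattern if control has the 6, and a possible enhancement signal if HCIP has them. At 125 per arm, with the same 40% rate, P(at least 6 ARDS cases) is:
- 13% / 6.5%: control (n = 16) 0.67. HCIP (n = 8): 28 × 0.4^6 × 0.6^2 + 8 × 0.4^7 × 0.6 + 0.4^8 = 0.050.
- 20% / 5%: control (n = 25) 0.97. HCIP (n = 6): 0.4^6 = 0.004.

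The protocol presents 40% as a worst case, so these ARDS figures illustrate why arm identity matters. They are not forecasts.

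**The case against.** **Masked may simply mean coded arms, A and B.** The protocol does not say so, and coded arms would still conflict with the general rule. The point does stand against part of the SAP evidence: analysis by treatment group is compatible with coded groups. The Randomization and Stopping guidelines sections are the firmer support.

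**Other safeguards remain.** This is correct, and it limits the harm. Section 8.3 halts enrolment and dosing for an unexpected infusion-related death or one unexpected SAE associated with study product. Each death is assessed for its relation to the plasma. A large imbalance in deaths would prompt unmasking even under the masked wording. The SAP's unmasked statistician can inform the DSMB.

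**The charter may settle it.** The charter was not supplied, and section 8.1 (Monitoring Plan) is not in the text available. Either could state the intended rule, but neither would make section 8.3 consistent with itself.

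**Stronger readings that a reader might infer.**
- *Masking would hide an equal split.* It would not. A board shown 2 and 2 deaths knows that HCIP has two, whichever code it carries, and can apply the two-death consideration.
- *Four ARDS cases in HCIP would be a signal missed.* Table 4 gives 0.430 in control and 0.026 in HCIP, but only for 15 and 4 cases. At the 50% review the same two-sided exact test gives about 0.72 in HCIP with 8 cases and 0.23 with 6, so four cases would not be unusual.
- *The board is left blind to harm.* Both sentences ask about a difference between arms, so the board must see counts by arm. Only the arm labels are withheld.

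**Conclusion.** Section 8.3 is wrong as written: its general rule and its two 50% reviews give opposite instructions on DSMB masking, and nothing in the supplied text reconciles them. The practical loss is arm identity in unequal splits too small to prompt unmasking. For deaths, the HCIP and control probabilities of two or more differ in every scenario examined (0.001 vs 0.018, 0.005 vs 0.021, 0.003 vs 0.048). These rest on the protocol's 1.4% fatality and its assumed attack rates. For ARDS the case rests on which arm has the larger count, under a worst-case 40% rate.

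A reader might infer a serious gap in safety oversight or a threat to the efficacy analysis. The documents support neither. The two-death consideration is advisory, the other safeguards operate throughout, and type I error, sample size and the primary analysis are untouched. This is an operational inconsistency of limited effect that should be corrected because the correction is so cheap.

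**What to change.** In the death paragraph of section 8.3, delete the word masked and the closing clause that makes unmasking conditional on a perceived difference. In the ARDS paragraph, delete the word masked. Both counts then go by identified arm to an unmasked DSMB, in line with the section's own general rule and with the SAP's Randomization and Stopping guidelines sections. Confirm that the DSMB charter says the same. If the sponsor did intend a masked first look, the general rule must be amended instead, and the plan must say how the intervention-arm consideration would then be applied.

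The cost is a few words in two sentences and one check against the charter. No extra data or staff are needed, since the SAP already provides an unmasked statistician who may inform the DSMB.

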Another theoretical risk is that antibody administration to those exposed to SARS-CoV-2 may avoid disease but modify the immune response such that those individuals mount attenuated immune responses, which would leave them vulnerable to subsequent re-infection. In this regard, passive antibody administration before vaccination with respiratory syncytial virus was reported to attenuate humoral but not cellular immunity [Crowe JE, Firestone C-Y, and Murphy BR. Passively acquired antibodies suppress humoral but not cell-mediated immunity in mice immunized with live attenuated respiratory syncytial virus vaccines. *The Journal of Immunology*. 2001; 167(7):3910-8.]. This concern will be investigated as part of this clinical trial by measuring immune responses in those exposed and treated with convalescent plasma to prevent disease. If the concern proved real these individuals could be vaccinated against COVID-19 when a vaccine becomes available.

Passive antibodies are derived from human plasma. The antibodies used in this study will be derived from plasma obtained from convalescent patients, and will be subjected to testing protocols that are similar to those used by blood banks and transfusion services. However, as is the case with any biological product, there is a very small risk of allergy/anaphylaxis, transfusion related acute lung injury (TRALI), and transfusion associated circulatory overload (TACO) or passive transfer of potential unknown infectious agents or infections. Most adverse effects are mild and transient including headaches, flushing, fever, chills, fatigue, nausea, diarrhea, blood pressure changes and tachycardia. Late adverse events are rare and include acute renal failure and thromboembolic events.

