4.5. Study drug administration

- Drug will be administered within 24 hours of randomization
- Transfusions for Johns Hopkins site participants will be performed at HEIC and Blood Bank approved JHM locations such as: 1) The Adult Clinical Research Unit (CRU) on Blalock 3 at Johns Hopkins Hospital and 2) the Neurosciences Consultation and Infusion Center at [name].
- If infusion takes place at the Adult CRU, Adult CRU registered nurses (RN's) will administer the infusion per JH policy. They will attend to the participant throughout the infusion and post infusion observation period. For infusion at any HEIC approved JHM location, registered nurses (RN's) from Johns Hopkins will administer the infusion per JH policy. They will attend to the participant throughout the infusion and post infusion observation period. All RNs are BLS trained. A study physician or advanced practice clinician with clinical privileges at JH will be available by phone and within 5 minutes physical response time to respond to any emerging event during the infusion.
- For non-Johns Hopkins sites, infusion will take place in the area designated for this research project. All infusions will be performed and monitored by appropriate personnel as defined by institutional policy for blood product transfusion.
- Infusion rate \leq 500 mL/hour
- Vital signs will be taken immediately prior to infusion, 10-20 minutes after start of infusion, at completion of infusion, and 30-60 minutes after the end of the infusion.

- Medicines for transfusion reactions (e.g. acetaminophen, diphenhydramine) may be given.
- If an AE develops during infusion, the infusion may be slowed or stopped as per investigator or infusion monitor decision.
 - Management of transfusion-associated AE will follow AABB guidelines; Outside of a simple allergic transfusion reaction, the transfusion will be discontinued and investigated appropriately (i.e. per standard practice guidelines).

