Table 3: Binomial Probability of at least one ARDS case among each treatment arm for a worse case scenario of 40 and 50% of those developing symptoms progressing to ARDS

Proportion Developing ARDS	Standard Plasma arm Expected Symptomatic N=15 participants	Anti-SARS-CoV-2 Plasma arm Expected Symptomatic N=4 participants
40%	>0.999	0.870
50%	>0.999	0.938

Table 4: For a given number of observed ARDS cases among the control plasma and anti-SARS-CoV-2 plasma treatment arms, the point estimate, 95% confidence interval, and probability of ARDS occurring under an assumed true rate of 0.4 among those who become symptomatic

	Standard Plasma Arm	Anti-SARS-CoV-2 Plasma arm
--	----------------------------	-----------------------------------

# of ARDS	Point Estimate of ARDS	95% Confidence Interval	Probability of occurring under true ARDS rate of 0.40	Point Estimate of ARDS	95% Confidence Interval	Probability of occurring under true ARDS of 0.40
1	0.07	(0.002, 0.319)	0.007	0.25	(0.006, 0.806)	>0.99
2	0.13	(0.017, 0.405)	0.036	0.50	(0.068, 0.932)	>0.99
3	0.20	(0.043, 0.481)	0.186	0.75	(0.194, 0.994)	0.309
4	0.27	(0.078, 0.551)	0.430	1.00	(0.398, 1.00)	0.026
6	0.40	(0.163, 0.677)	>0.99			
9	0.60	(0.323, 0.837)	0.122			
10	0.67	(0.384, 0.882)	0.061			

Upon completion of this review and receipt of the advice of the ISM or SMC, it will be determined if study entry or study dosing should be interrupted or if study entry and study dosing may continue according to the protocol.

Halting Criteria/Rules for Subject Infusion

Infusion of study drug will be halted if any of the following manifestations of anaphylaxis develop and will not be restarted:

- Skin or mucous membrane manifestations: hives, pruritus, flushing, swollen lips, tongue or uvula
- Respiratory compromise: dyspnea, wheezing, stridor, hypoxemia
- A decrease in systolic blood pressure to < 90 mmHg or >30% decrease from baseline or a diastolic drop of >30% from baseline.
- Tachycardia with an increase in resting heart rate to > 130bpm; or bradycardia <40 that is associated with dizziness, nausea or feeling faint.

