- Syncope
- Confusion
- Any other symptom or sign which in the good clinical judgment of the study clinician or supervising physician warrants halting the infusion. For example, the rapid onset of gastrointestinal symptoms, such as nausea, vomiting, diarrhea, and cramps, for instance, may be manifestations of anaphylaxis and may warrant an immediate halt prior to meeting full SAE criteria

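### For isolated hives or itching (and flushing, if classed as allergic), protocol sections 4.5 and 8.3 give inconsistent rules on stopping the infusion, and nothing says which governs

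*Protocol*

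**What the plan says.** Protocol section 4.5 (Study drug administration) gives a general rule: "If an AE develops during infusion, the infusion may be slowed or stopped as per investigator or infusion monitor decision". A sub-item beneath it refers management of transfusion-associated events to AABB guidelines and adds: "Outside of a simple allergic transfusion reaction, the transfusion will be discontinued and investigated appropriately". A simple allergic reaction is thus outside the mandatory stop and falls back on the discretionary rule. The same section says: "Medicines for transfusion reactions (e.g. acetaminophen, diphenhydramine) may be given".

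Protocol section 8.3, in its closing part on halting an individual infusion, states: "Infusion of study drug will be halted if any of the following manifestations of anaphylaxis develop and will not be restarted". The first entry on the list is: "Skin or mucous membrane manifestations: hives, pruritus, flushing, swollen lips, tongue or uvula". Respiratory, blood-pressure, heart-rate and neurological signs follow. The last entry is a catch-all: "Any other symptom or sign which in the good clinical judgment of the study clinician or supervising physician warrants halting the infusion". Fever and chills are not listed.

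Protocol section 3.2, in a background account of transfusion risks, says: "Most adverse effects are mild and transient including headaches, flushing, fever, chills". Section 4.4 intends every participant to receive at least 175 mL (one unit). Section 4.5 caps the rate at 500 mL/hour and schedules a vital-sign check 10 to 20 minutes after the start.

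**The concern.** Consider a participant who develops hives or itching during the infusion and nothing else. Staff working from section 4.5 may treat this as a simple allergic reaction, slow the infusion, give an antihistamine and finish the unit. Staff working from section 8.3 must halt and may not restart. The protocol thus allows two different courses for the same sign.

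Three things are at stake. The first is a participant-safety instruction that should read the same wherever it appears. The second is the delivered dose, which may be a full unit under one section and must be a truncated one under the other. The third is uniformity across sites: section 4.5 has non-Johns Hopkins sites infuse and monitor with personnel defined by their own institutional policy, so an ambiguity in the protocol can be settled differently from site to site. Severe infusion reactions also form part of a primary safety endpoint, which is a further reason to handle reactions uniformly.

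**Working it through.** There is no planned figure to reproduce. The check is a comparison of the text, with one piece of arithmetic on volume.

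**Step 1. Apply both sections to each sign, occurring alone.**

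| Sign | Section 4.5 | Section 8.3 | Result |
|---|---|---|---|
| Hives or itching, judged simple allergic | Discretion to slow or stop | Mandatory halt, no restart | Inconsistent |
| Flushing, classed as allergic | Discretion to slow or stop | Mandatory halt, no restart | Inconsistent |
| Flushing, transfusion-associated but not classed as allergic | Mandatory discontinuation | Mandatory halt, no restart | Both stop |
| Fever or chills, judged transfusion-associated | Mandatory discontinuation | Not listed; left to judgment | Different force |

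**Step 2. Ask whether the reference to anaphylaxis separates the cases.** Section 8.3 calls its signs manifestations of anaphylaxis, so it might be meant only for suspected anaphylaxis. The one place that describes anaphylaxis is item II of the study-level halting criteria in the same section. There it is a life-threatening reaction with bronchospasm, with or without urticaria or angioedema, needing pressors or ventilation. If that meaning carried over, skin signs alone could never trigger a halt and the skin entry would do no work. The catch-all entry also contemplates halting before full SAE criteria are met, so the list appears designed to act early. No text tells staff when hives are a simple allergic reaction and when they are a sign of anaphylaxis.

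**Step 3. Look for an order of precedence.** Neither section refers to the other, and the protocol text available to me does not say which governs.

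**Step 4. Test each action against both sections, for isolated hives judged simple allergic.**

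- Stop permanently: permitted by 4.5, required by 8.3. Complies with both.
- Slow and continue: permitted by 4.5, breaches 8.3.
- Pause and restart: not forbidden by 4.5, breaches 8.3.

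**Step 5. Volume delivered after a permanent stop.** The inputs are the 500 mL/hour ceiling, the 10 to 20 minute check and the 175 mL minimum.

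- Shortest time to 175 mL: 175 / 500 × 60 = 21 minutes.
- Most delivered by 10 minutes: 500 × 10 / 60 = 83 mL.
- Most delivered by 20 minutes: 500 × 20 / 60 = 167 mL.

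A permanent stop at that check therefore always leaves less than 175 mL, even at the maximum rate. This is an illustration: it assumes that the reaction is noticed at that check.

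**Step 6. Effect on the analysis.** The SAP's modified intention-to-treat set excludes only those who do not initiate the infusion, so a participant with a truncated unit stays in. The SAP's per-protocol sensitivity analysis defines non-adherence by receipt of the wrong product, so it does not address a partial volume.

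**The case against.** The strongest reply is that the sections cover different diagnoses: 4.5 a simple allergic reaction, 8.3 anaphylaxis. Section 4.5 also points to AABB guidelines and institutional transfusion policy, which may draw the line between them. This reading is possible, and those sources cannot be seen from the documents. What does not stand is that the protocol itself makes the distinction: its halting list names hives, itching and flushing without qualification, and any one of them suffices.

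A reader might go further and infer that the sections give opposite instructions, that no site can comply with both, and that a protocol deviation is unavoidable. The documents do not support this. Section 4.5 is permissive and nowhere orders the infusion to continue, so a permanent stop satisfies both sections. The difference is between a discretionary and a mandatory stop.

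A reader might also see a contradiction over fever and chills. Section 8.3 does not list them and leaves unlisted signs to judgment, while 4.5 requires discontinuation of transfusion-associated events that are not simple allergic. That is a difference in force, and discontinuing satisfies both. Within 4.5, the discretionary rule for any adverse event followed by a stricter one for transfusion-associated events can be read as general and specific.

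Nor does the background statement in section 3.2 prove a conflict, since a usually mild sign can still prompt a precautionary stop. Allowing an antihistamine does not imply that the infusion continues. Finally, both arms receive plasma under masking and randomization is stratified by site, so nothing in the documents points to an effect that differs by arm.

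**Conclusion.** The concern holds in a narrow form. For isolated hives or itching, and for flushing if it is classed as allergic, section 4.5 leaves stopping to discretion and section 8.3 requires a halt without restart. The protocol supplies neither a working distinction between the two situations nor an order of precedence. A site that uses the exemption in 4.5 breaches 8.3, and the participant's chance of receiving the full unit depends on the section followed.

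The conclusion rests on the wording alone and needs no assumed rate. Its size cannot be stated in participants: the documents give no frequency for these reactions, and nothing in them supports calling these the commonest ones. A truncated unit can also arise under 4.5, which permits stopping. The consequence for the primary analysis is limited, because initiating the infusion determines inclusion. This is an inconsistency in a safety and dosing instruction that should be corrected, and it does not threaten the validity of the primary comparison.

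The differing treatment of fever and chills is a secondary point to settle in the same revision.

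**What to change.** Reconcile section 4.5 with the individual-infusion part of section 8.3 into one infusion-reaction rule, stated once and cross-referenced from the other place, so that both give the same answer for the same sign. The rule should cover:

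- isolated skin or allergic signs;
- fever or chills;
- the respiratory, haemodynamic and neurological signs already listed in 8.3.

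For each it should say whether the infusion is slowed, paused or permanently stopped, and whether that is mandatory or left to judgment. If a simple allergic reaction is to be handled differently from suspected anaphylaxis, the text should say how staff tell them apart. Which clinical rule applies is for the sponsor to decide; no view is taken here.

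The cost is a protocol wording amendment and a memo to sites. No procedures or participants are added.
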